Pain control during and after abortion is a Society of Family Planning priority. Pain management regimens for surgical abortion can rely on local anesthetic, oral analgesics, moderate sedation, deep sedation, or a combination of approaches. While several recent studies have attempted to reduce pain with adding supplemental medications or therapies, such as nonsteroidal anti-inflammatory drugs, narcotics, anxiolytics, misoprostol, nitrous oxide, music, most studies have failed to improve pain scores. As optimal pain management has not been established, many women continuing to report moderate to severe pain during and after the procedure [1].

We propose a novel regimen of oral gabapentin administered prior to usual pain management regimens for surgical abortion. Gabapentin is used to treat neuropathic and chronic pain. Mechanism of action may include calcium channel blockade and modulation of nociceptive neurotransmitters. Clinical trials support use of perioperative gabapentin to reduce post-surgical pain in a variety of clinical settings[2]. Gabapentin is well-tolerated and inexpensive, with mild, if any, side effects. [3] In a systematic review of 22 randomized controlled trials (RCT) of multiple surgical procedures including ambulatory nasal surgery, orthopedic procedures and laparotomy, a single preoperative dose of gabapentin significantly reduced 24-hour opioid consumption[3]. Perioperative gabapentin before hysterectomy showed reduced pain scores, nausea and vomiting [4, 5] A randomized trial in the setting of cesarean showed improved pain scores and decreased pain requirements with a 600 mg dose of preoperative gabapentin [5]. Its use in the setting of abortion has never been evaluated.

We hypothesize that adding gabapentin preoperatively to current pain management regimens will reduce pain associated with surgical abortion. Additionally, we hypothesize that preoperative gabapentin will reduce perioperative nausea, vomiting and anxiety with few adverse effects.

Primary Aim: To evaluate the impact of adjunctive preoperative gabapentin on perioperative pain during uterine aspiration <15 weeks of gestation for abortion and pregnancy loss management compared to usual pain control regimens

Secondary Aims

- To evaluate the impact of preoperative gabapentin on:
 - perioperative nausea and vomiting
 - preoperative anxiety
 - use of pain medications and anti-emetics post-operatively

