- To evaluate side effects or adverse events of gabapentin in this setting
- To identify subgroups where adjunctive gabapentin may be more effective at reducing perioperative pain such as gestational age ranges and patient characteristics (age, gravidity, substance abuse, preoperative anxiety level).

Background and Rationale:

Surgical abortions in North America are typically performed using either local anesthetic with oral analgesics or moderate sedation. A 2009 Cochrane review of evidence for pain control assessed that paracervical block in reducing abortion related pain is limited, while the addition of ibuprofen and naproxen can slightly reduce intraoperative and post operative pain [6]. Evidence supports the benefit of conscious sedation at reducing intraoperative and post-operative pain in abortions [7]. General anesthesia can be useful in some settings, however its use is limited due to cost, staffing and potential for additional risks. Further, studies have found, although better at reducing pain during the procedure, general anesthesia is not superior to moderate sedation for post-operative pain [8]. Other recently examined adjuncts to pain control have not proven to be beneficial in this setting [9-11].

Gabapentin is widely used to treat neuropathic and chronic pain. Mechanism of action may include calcium channel blockade and modulation of nociceptive neurotransmitters. Clinical trials support use of perioperative pregabalin and gabapentin to reduce perioperative and post-operative pain in a variety of clinical settings, for both major and minor surgical procedures [2, 12]. While pregabalin has a faster peak plasma concentration, gabapentin is a less expensive option with peak concentrations reached by 2 hours, with substantial evidence to support routine use and safety in reducing perioperative pain. In a systematic review of 22 randomized controlled trials (RCT), a single preoperative dose of gabapentin significantly reduced 24-hour

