600 mg of gabapentin was selected as a well-tolerated intermediate dosage with benefit proven in prior perioperative pain studies. The window of 1-2 hours is consistent with preoperative dosing in other studies and can allow for its co-administration with misoprostol, and allows for some variability that is practical with a busy clinic.

Study Procedures:

All recruitment, screening and enrollment questions will be asked by trained study staff in a private room.

Recruitment:

We will be recruiting a total of 96 women, with equal allocation to the invention group and placebo. The proposed research will take place at Duke Ryan Clinic, at the Duke gynecology outpatient clinic. Women who attend Duke for a uterine aspiration will have their preoperative evaluation and over the phone counseling. During this call, the clinical provider will introduce the study to the patient to determine interest in participating in the study. All patients are scheduled and given standardized pre-procedure counseling by our clinic coordinator. If the patient is interested in possible participation, study personnel will be notified. The study team will then contact the patient to provide them with information about the study. A standard recruitment script will be employed (Appendix A).

Screening and consent:

For individuals who are interested in participating, we will screen for eligibility using an eligibility checklist (Appendix A). Those eligible after screening will review the informed consent and sign consent forms prior to the final clinical preoperative review. Patient contact information will be collected at this time. After the nurse reviews the medical chart, randomization will occur and intervention will be received.

Randomization, Allocation Method and Blinding:

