We will collect baseline demographics, medical history (gravidity, parity, prior abortions (medical and surgical), gestational age, drug and alcohol use, psychiatric or sexual assault history), medications used at home and given at the clinic preoperatively, indication for procedure (personal/social, fetal or maternal health)).

Study Size and Power:

We will enroll a total of 96 women. Assuming a standard deviation of 26 mm on the 100-mm visual analog scale (VAS), based on prior studies, this will provide us with an 80% power, using a p-value of 0.05, to detect a 15 point difference in pain among all participants. A difference of 15-20 mm has been assessed to be clinically meaningful in prior studies. Given that our primary outcome will be measured immediately after the procedure, our loss to follow-up will be minimal. A 100-mm pain visual analog scale has been shown to be useful for the evaluation of pain in prior pain abortion research [5, 6] with a mean standard deviation in previous studies of approximately 26 mm [5]. We are assuming no loss-to-follow-up as our primary outcome will be measured at the time of the procedure.

Data Management and Analysis

Data Management:

Prior to study initiation, a database will be developed using a web-based password-protected relational database (REDCap). All data will be collected will be recorded on clinical research forms (CRFs) and entered into the database at the end of each day. All CRF source documents will be filed and stored for future reference. See monitoring and oversight section below for further details on procedures and protections.

Analytic Plan:

We will compare groups on the primary continuous outcome measure (pain score on 11-point VAS) using T-tests. Chi-square and T-tests will be used to evaluate secondary outcomes for categorical and continuous variables, respectively. Baseline characteristics will be evaluated for potential interaction or confounding with primary and secondary outcomes.

Upon study completion at each site for the prospective meta-analysis, data from each site will contribute to the final meta-analysis using criteria outlined in the Cochrane Handbook for Systematic Reviews of Interventions. Site RCT publications will mention contribution to this PMA. Subgroup analyses will address gabapentin adjunct to local anesthesia and moderate sedation, as well as by specified population characteristics and gestational age.

Ethical Concerns

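### Side effects are compared by a chi-square test alone, with no risk difference or interval, and a non-significant result at 48 per arm cannot by itself support the hypothesis of few adverse effects

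*Combined protocol and SAP*

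**What the plan says.** The hypothesis paragraph ahead of the Primary Aim reads: "we hypothesize that preoperative gabapentin will reduce perioperative nausea, vomiting and anxiety with few adverse effects". The Secondary Aims carry this forward in neutral terms: "To evaluate side effects or adverse events of gabapentin in this setting". Under Secondary Outcomes, side effects are recorded on a checklist before discharge and asked about again in the call on the next day. The draft questionnaire prints the checklist in the 10-minute post-operative form: six symptoms, each graded none, mild, moderate or severe.

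The Analytic Plan has one sentence on secondary outcomes: "Chi-square and T-tests will be used to evaluate secondary outcomes for categorical and continuous variables, respectively". It names no risk difference, confidence interval or definition of few, and does not say how the four grades enter the test. Study Size and Power concerns VAS pain only: "We will enroll a total of 96 women", giving "80% power, using a p-value of 0.05, to detect a 15 point difference in pain among all participants".

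Safety is also reviewed while the trial runs. The Adverse events section provides a medical monitor, and there is a Data Monitoring Committee. Site data later enter a prospective meta-analysis with 4 other sites.

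**The concern.** A hypothesis that a drug lowers pain is supported when a test rejects no difference. A hypothesis that it brings few adverse effects works the other way. A non-significant test may mean that there is little excess, or that the trial was too small to see it, and the p-value does not tell the two apart. The smaller the trial, the easier a non-significant result is to obtain.

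At stake is the site's own report on a stated secondary aim. A real rise in dizziness or somnolence among outpatients could appear as no significant difference and be taken as confirming good tolerability. The background already describes the drug as well tolerated with mild side effects if any, so that reading would come easily. The primary pain analysis is not affected.

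**Working it through.** **Inputs from the documents.** 96 women in total (Study Size and Power). Allocation is equal (Recruitment: "with equal allocation to the invention group and placebo"), so 48 per arm. SD 26 mm, difference 15 mm, power 80%, alpha 0.05, no loss to follow-up. Sidedness is not stated; two-sided is taken here because it reproduces the sample size.

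**Assumed, not in the documents.** The placebo rate of a given side effect; each checklist item reduced to yes or no; no continuity correction.

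**Step 1: the plan's own figure.** n per arm = 2 × (1.960 + 0.842)² × 26² / 15² = 47.2, rounded up to 48, so 96 in total. The sample size reproduces. It was set by pain alone.

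**Step 2: chance of missing a 20-point rise.** The Pearson statistic is (difference in proportions)² / [p̄(1 − p̄) × 2/48], where p̄ is the pooled proportion. It is significant at or above 1.96². The table sums the probabilities of all non-significant outcomes of two independent binomials with n = 48 each. The last column does the same for the more conservative tests.

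| Placebo vs gabapentin | Missed, uncorrected chi-square | Missed, Yates or Fisher |
|---|---|---|
| 5% vs 25% | 16% | 28% |
| 10% vs 30% | 28% | 39% |
| 15% vs 35% | 37% | 46% |
| 20% vs 40% | 41% | 51% |
| 30% vs 50% | 48% | 57% |
| 40% vs 60% | 49% | 57% |

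For a 15-point rise, the uncorrected test misses 49% (10% vs 25%), 62% (20% vs 35%) and 67% (30% vs 45%).

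**Step 3: what an interval would show.** Take an illustrative 18/48 on gabapentin and 10/48 on placebo, that is 37.5% vs 20.8%.

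- Test: p̄ = 28/96 = 0.292. The statistic is 0.1667² / (0.292 × 0.708 × 2/48) = 3.23, p = 0.072, not significant.
- Wilson 95% limits: 25.2% to 51.6% on gabapentin, 11.7% to 34.3% on placebo.
- Newcombe lower limit: 16.7 − √[(37.5 − 25.2)² + (34.3 − 20.8)²] = 16.7 − 18.2 = −1.5 points.
- Newcombe upper limit: 16.7 + √[(51.6 − 37.5)² + (20.8 − 11.7)²] = 16.7 + 16.8 = 33.5 points.

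The test alone reports no significant difference. The interval shows that an excess of about one woman in three has not been excluded.

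**Step 4: precision when the arms look alike.** With 5/48 in each arm the Newcombe upper limit is 13.1 points; with 10/48 in each it is 16.2 points. Even identical observed rates leave a double-digit excess open.

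**The case against.** The strongest reply is that few adverse effects is ordinary language about how often events occur on gabapentin, not a non-inferiority claim against placebo. The aim is worded neutrally, and the graded checklist would let the frequency and severity on gabapentin be described directly. That reading is available, and it stands. It does not close the gap. The plan does not say that frequencies will be reported by grade, it does not define few, and the only comparison it names is a bare test.

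A reader might infer that the plan treats p > 0.05 as proof of safety. It does not say so. The risk is a misreading that the plan leaves open, not one that it prescribes.

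A reader might also infer that the test is the only safety provision. That is wrong: the medical monitor, the committee and the meta-analysis all exist. But the monitor and the committee protect participants during conduct and have no numerical criterion. Under Problems Anticipated, this site will publish whether or not other sites finish. None of these provisions gives a between-arm interval for its report.

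The miss rates depend on assumptions, and a 20-point rise made up wholly of mild symptoms need not contradict few adverse effects. Both points stand, and the second is a reason to show grades.

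Finally, it is tempting to require a fixed acceptance margin. The case against that stands. With a 20-point margin and no true excess, the Newcombe upper limit at 48 per arm falls below the margin 87%, 70% or 60% of the time, for rates of 10%, 20% or 30%. With a true 10-point excess it does so 19% to 28% of the time. Each figure is for one symptom, and there are six. Such a rule would often end as inconclusive, and choosing the margin takes clinical judgement.

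**Conclusion.** The point holds in a limited form. The plan hypothesises few adverse effects, names only a test of difference for categorical side effects, and provides no estimate or interval. With 48 per arm, a non-significant result cannot by itself support the hypothesis. That follows from the logic of the test at any side-effect rate.

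The size is conditional. For an assumed placebo rate of 10% to 30%, a yes/no outcome and an uncorrected test, a 20-point rise is missed about 28% to 48% of the time. At a 5% placebo rate it is 16%; with Yates or Fisher the figures are higher, up to 57%. These are not properties that can be read off the documents. Nor do the documents support the view that the trial is invalid for want of a margin. The matter concerns analysis and reporting of a secondary aim, and the remedy is nearly free.

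**What to change.** In the Analytic Plan, add for each side effect:

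- the number and percentage by arm and by grade;
- the risk difference, gabapentin minus placebo, with a 95% Newcombe interval, stating which grades count as an event;
- a statement that a non-significant test alone will not be taken as support for few adverse effects, and that the conclusion will cite the upper limit of the excess not excluded.

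A formal acceptance margin is optional and for the sponsor to decide. If one is used, it should be fixed before unblinding.

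The cost is one or two sentences, with no new data and no more participants. The drawback is that the report may have to make a weaker statement, namely that an excess of up to so many points cannot be excluded.

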Women undergoing a procedure who meet study inclusion criteria and complete informed consent will be eligible for participation. *Randomization* will be done using computer-generated random numbers (randomization.com) in variable blocks of 8 and 10. *Allocation* concealment will be maintained by identically labeled sealed sequentially numbered opaque pill containers. Gabapentin and placebo tablets will be indistinguishable by appearance, thus maintaining blinding for participants and assessors. To maintain double *blinding* for both investigators and participants, an individual not associated with study conduct will create the randomization sequence and allocation containers. The randomization assignments will only be revealed at the point of data analysis or if an interim assessment is needed.

Enrollment:

After the final perioperative clearance, the individual will be randomized and receive their method allocated by the clinic nurse. The study staff will review the enrollment questionnaire that includes demographic questions. Following completion of the questionnaire, the participant will wait before moving to our procedure room (this will occur approximately 1-2 hour after nursing review and receipt of the study intervention). Prior to initiating the procedure, study staff will administer the preoperative questions. The physician will then complete the uterine aspiration while the study staff remains outside of the operative room. Immediately following the procedure, the study staff will then administer the immediate post-operative questions and follow the participant to the recovery room to complete the remaining questions assessed at 5 minutes, 10 minutes, 30 minutes and at discharge. When the discharge questions are complete, the

participant will receive a \$20 gift card and instructed to expect a follow-up call the following day.

Follow-up:

On the day following the procedure (approximately 24 hours after the procedure), study staff will call the participant to complete the follow-up questions. On completion of the questions, an additional \$10 will be transferred to the gift card.

Withdrawals, losses and deviations:

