Randomization to study method will occur after completion of all intake forms and consent, immediately before the pill is to be taken, thus reducing the possibility of withdrawal after randomization. Primary outcome measures and most secondary outcome measures will be assessed immediately before, during or after the abortion procedure, thus any loss to follow-up will be limited to those who consent to, but change their mind while waiting for their procedure. Based on current clinical practice at this clinic, withdrawal after consent is extremely rare. Our secondary outcomes assessed post-operatively after discharge will be collected via the phone. We will maximize completion of these assessments through the following steps: participants will be told beforehand about the telephone contact following the procedure, a cellular telephone number will be collected and tested at the clinic, a secondary phone number and email will be collected as a backup, participants will be given a contact number for the study coordinator should they have any challenges with receiving a phone calls, and participants will receive an additional \$10 sent to their gift-card following the completion of their phone assessment.

Data Collection/Outcome measurements:

Outcome measures and baseline variables are described in Table 1.

Primary study outcome

Our primary outcome measure will be pain score using an 100-mm visual analog scale (VAS) measured 5 minutes after removal of the speculum.

Secondary Outcomes:

We will also be measuring pain on the 100-mm VAS preoperatively immediately prior to the procedure, after the procedure, 10 minutes and 30 minutes following the procedure and at discharge. Nausea, using a VAS, and vomiting will be assessed preoperatively immediately prior to the procedure and post operatively at 10 minutes, 30 minutes and at discharge. Anxiety prior to the procedure will be measured using the preoperative state trait anxiety inventory. Side effects will be assessed using a checklist prior to discharge. We will also be contacting participants on post-operative day 1 to assess pain, nausea, vomiting, side effects and general satisfaction with the procedure (on a 5-point scale). The quantity and type of medications used perioperatively and post-operatively including medications used at home in the 24 hours post-operatively will be abstracted from the clinical record and assessed on the phone.

Baseline Characteristics and covariates:

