You answer the question by making a hash mark on the line according to how much you like or dislike Oreo cookies.

If you liked Oreo cookies a lot, then you might make a hash mark on the line like so:

very
little

very
much

If you liked Oreo cookies more than life itself(!), then you might make a hash mark on the line like so:

very little _____ |

very
much

If you hated Oreo cookies, then you might make a hash mark like so:

very
little

very
much

If you thought Oreo cookies were just "OK," then you might make a hash mark like so:

very
little

very
much

The idea is that if you like Oreo cookies, you make a hash mark on the line closer to the phrase "very much;" the closer you make the hash mark, the more you are saying you like Oreo cookies. If you don't like Oreo cookies, you make a hash mark on the line closer to the phrase "very little;" the closer you make the hash mark, the more you are saying you don't like Oreo cookies.

1. Make a hash mark on the line to indicate how nervous you feel about the surgery you are about to have.

NOT
NERVOUS _____

VERY NERVOUS

2. Make a hash mark on the line to indicate how nervous you feel about the pain you will experience during your procedure.

NOT
NERVOUS _____

VERY
NERVOUS

3. Make a hash mark on the line to indicate how much pain you expect to have during your abortion procedure.

NO
PAIN _____

WORST PAIN
IN MY LIFE

4. Make a hash mark on the line to indicate how much pain you have waiting for your procedure to start.

NO
PAIN _____

WORST PAIN
IN MY LIFE

5. Make a hash mark on the line to indicate how much nausea you currently have

NO
NAUSEA _____

WORST NAUSEA
I HAVE EVER HAD

Have you vomited since you received your study medication?

NO YES

State Trait Anxiety Inventory[1]

Read each statement and select the appropriate response to indicate how you feel right now, that is, at this very moment. There are no right or wrong answers. Do not spend too much time on any one statement but give the answer which seems to describe your present feelings best.

		Not at all	A little	Somewhat	Very much so
1	I feel calm	1	2	3	4
2	I feel secure	1	2	3	4
3	I feel tense	1	2	3	4
4	I feel strained	1	2	3	4
5	I feel at ease	1	2	3	4
6	I feel upset	1	2	3	4
7	I am presently worrying over possible misfortunes				
8	I feel satisfied	1	2	3	4
9	I feel frightened	1	2	3	4
10	I feel uncomfortable	1	2	3	4
11	I feel self confident	1	2	3	4
12	I feel nervous	1	2	3	4
13	I feel jittery	1	2	3	4
14	I feel indecisive	1	2	3	4

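### Anxiety subgroup: the only pre-procedure anxiety score in the available text is taken 1-2 hours after the study pill, so strata formed from it would not be randomised comparisons

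*Combined protocol and SAP*

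**What the plan says.** The last of the Secondary Aims is to find subgroups in which gabapentin reduces pain more, "such as gestational age ranges and patient characteristics (age, gravidity, substance abuse, preoperative anxiety level". Anxiety level stands there beside age and gravidity as a characteristic of the patient.

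The same quantity is also an outcome. The hypothesis reads "Additionally, we hypothesize that preoperative gabapentin will reduce perioperative nausea, vomiting and anxiety with few adverse effects", preoperative anxiety is a secondary aim in its own right, and the Secondary Outcomes section states "Anxiety prior to the procedure will be measured using the preoperative state trait anxiety inventory".

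The Enrollment section gives the order of events. The nurse gives the allocated pill after randomisation, and the woman waits before going to the procedure room ("this will occur approximately 1-2 hour after nursing review and receipt of the study intervention"). Then "Prior to initiating the procedure, study staff will administer the preoperative questions".

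The Preop Assessment in the draft questionnaire contains the nervousness lines, the first being "Make a hash mark on the line to indicate how nervous you feel about the surgery you are about to have", and a 20-item inventory of present feelings. It also asks whether the woman has vomited since taking the study medication, which confirms that it follows the pill.

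The section on baseline characteristics and covariates lists psychiatric history but no anxiety score. Question 12 of the draft questionnaire records anxiety as a yes/no condition, with any medication for it. The outcome section adds "Outcome measures and baseline variables are described in Table 1"; that table is not in the text available for review.

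**The concern.** A subgroup analysis by a characteristic fixed before treatment keeps the protection of randomisation: within each stratum the arms differ only by chance and by treatment. That is lost when the variable is measured after treatment and treatment can change it. Here the plan itself predicts the change.

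If gabapentin calms women, some who would have scored high on placebo score low on gabapentin. The gabapentin women left in the high stratum were more anxious to begin with than the placebo women there, and the low stratum gains women who were more anxious to begin with. If more anxious women report more pain, an arm difference appears in both strata without any effect of the drug on pain.

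At stake is the reading of one secondary subgroup analysis. The same fault would arise if the post-pill score were used as an adjustment variable, since the Analytic Plan evaluates baseline characteristics for interaction and confounding without saying that they must predate the pill.

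**Working it through.** **The plan's own figure.** With SD 26 mm, difference 15 mm, two-sided 0.05 (sidedness is not stated) and 80% power, n per arm = 2 × (1.960 + 0.842)² × 26² / 15² = 47.2, rounded up to 48, so 96 in total. Power with 48 per arm is 80.7% (normal approximation) or 79.9% (t-test). The stated size reproduces and does not depend on the anxiety score.

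**Inputs for the illustration.** The SD of 26 mm and 48 women per arm are from the section on study size and power. The following are assumptions, not in the documents:
- the pill lowers the anxiety score by d = 0.3 to 0.5 SD
- the correlation of pre-pill anxiety with pain is ρ = 0.3 to 0.5
- strata are split at the pooled median of the post-pill score
- gabapentin has no true effect on pain

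**Model.** Pre-pill anxiety A is standard normal. Pain, as a deviation from its mean, is 26 × (ρA + √(1 − ρ²) × noise). The score is A on placebo and A minus the shift on gabapentin. The false difference in a stratum, gabapentin minus placebo, is 26 × ρ × (difference between arms in mean A within that stratum).

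**All women calmed equally.** The pooled median of the score is −d/2. The high stratum is then A > d/2 on gabapentin and A > −d/2 on placebo. For a standard normal, the mean of A above a cut a is φ(a) / (1 − Φ(a)).
- d = 0.3: means 0.3945/0.4404 = 0.896 and 0.3945/0.5596 = 0.705, difference 0.191. High stratum: 48 × 0.440 = 21.1 gabapentin and 48 × 0.560 = 26.9 placebo women.
- d = 0.5: means 0.3867/0.4013 = 0.964 and 0.3867/0.5987 = 0.646, difference 0.318. High stratum: 19.3 and 28.7 women.

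By symmetry the low stratum has the same difference. Multiplying by 26ρ (7.8 or 13):

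| d | ρ | False difference, each stratum (mm) | High minus low (mm) |
|---|---|---|---|
| 0.3 | 0.3 | 1.49 | 0 |
| 0.3 | 0.5 | 2.48 | 0 |
| 0.5 | 0.3 | 2.48 | 0 |
| 0.5 | 0.5 | 4.13 | 0 |

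**Only women above the pre-pill median calmed.** The same calculation by numerical integration, with the cut again at the pooled median:

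| d | ρ | High stratum (mm) | Low stratum (mm) | High minus low (mm) |
|---|---|---|---|---|
| 0.3 | 0.3 | 0.86 | 1.10 | −0.25 |
| 0.3 | 0.5 | 1.43 | 1.84 | −0.41 |
| 0.5 | 0.3 | 1.25 | 1.94 | −0.69 |
| 0.5 | 0.5 | 2.08 | 3.23 | −1.15 |

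Positive values in a stratum mean more pain on gabapentin. A negative contrast means that gabapentin looks relatively better in the high stratum.

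**Checks.** With d = 0 the two arms have the same cut and the false difference is 0. With no true effect, a split on a pre-pill value also gives 0, because both arms are cut on the same unaltered variable.

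**Scale.** With about 24 women per arm in a stratum, the standard error of the arm difference is 26 × √(2/24) = 7.5 mm. The largest false difference here, 4.1 mm, is 4.13 / 7.5 = 0.55 of that.

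**The case against.** The strongest objection is that the plan never says the post-pill score will form the strata. The Analytic Plan speaks of baseline characteristics, the inventory is listed as an outcome, and question 12 gives an anxiety history that the pill cannot change. Table 1 may list a pre-pill score, and the questionnaire is a draft. This stands as a limit: the documents do not show that a pre-pill score is absent from the study. It does not remove the point. The subgroup aim speaks of a level, a yes/no history is not a level, and the term used for the subgroup is the one used for the outcome.

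A second objection is that the sizes rest on assumed inputs and are small beside the sampling error of a stratum. That is correct, and they are offered only as an illustration.

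A reader might go further and infer that the contrast between strata would be badly diluted, with a marked loss of power. The documents do not support this. They give no cut-point, interaction size, model or reliability for the score. A sizeable dilution needs both a benefit that steps at the median and a score free of error. If benefit changes linearly with anxiety the contrast hardly moves, and if the score is imperfect a pre-pill split is itself diluted, so that timing adds little.

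Nor are both strata always biased against gabapentin. That holds for the no-effect case worked here. If only more anxious women benefit, calmed women who benefit move into the low stratum, which can then lean towards gabapentin.

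**Conclusion.** The point holds as a minor one. In the available text the only score that fits the subgroup term is recorded after the pill and is an outcome the pill is expected to lower. If it defines the strata and the drug does lower anxiety, comparisons of arms within strata are not randomised comparisons. A larger sample, in this trial or by pooling, would not remove that bias.

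Under the assumptions stated, the within-stratum error is a few millimetres against gabapentin, smaller than the standard error of a stratum. The contrast between strata, which is what the aim asks about, is little affected.

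It would be wrong to infer that the main result is compromised: the primary analysis is a t-test between randomised arms that does not use anxiety. It would also be wrong to infer that the pooled analysis is committed to this subgroup: the Analytic Plan's list for the meta-analysis does not name anxiety.

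**What to change.** Define the anxiety subgroup, and any adjustment for anxiety, only by a value recorded before the pill, and keep the pre-procedure inventory as an outcome only. Any one of these would do:

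- Ask the existing nervousness line (Preop Assessment, question 1) once more, after consent and before the pill. The text should say outright that it precedes the pill. Calling it an intake item is not enough, because the section on withdrawals says "Randomization to study method will occur after completion of all intake forms and consent, immediately before the pill is to be taken", whereas the Enrollment section has the enrollment questionnaire reviewed after the pill is received. Those two passages should be reconciled.
- Use the anxiety history in question 12.
- Remove anxiety level from the subgroup list in the Secondary Aims.

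If Table 1 already contains a pre-pill anxiety score, naming it in the Secondary Aims is enough. In every case the Analytic Plan should say that baseline characteristics are values recorded before the pill, or history that the pill cannot change.

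The cost is one or two minutes per woman, one added line on a form and small wording changes, with no extra participants. The drawback is that a single line or a yes/no history is coarser than the 20-item inventory, so a true difference between subgroups may be diluted. With the added line, women are also asked about nervousness twice, equally in both arms. Use in the pooled analysis would need the same item at the 4 other sites.
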